14.5 Sample Size Determination

Sample size has been determined based on an acceptable level of accuracy for the estimated rate of hernia recurrence at 12 months (primary endpoint).

Previous studies of the predicate device (Proceed™ Surgical mesh) with similar study indications, population, and design (prospective study with a long-term follow-up with more than 100 subjects), have reported the incidence of recurrence at 12 months to range from 3.5% to 5.2%. (8, 9).

95% confidence intervals obtained from incidence rates between 3.5% and 5.2% with N=100 subjects are shown below. Precision of the recurrence rates range from \pm 3.6% to \pm 4.4% as the recurrence rate increases.

	Recurrence rate at 12-month (1 year)						
	3.5%	4.0%	4.5%	5.2%			
N	100	100	100	100			
95% CI	[0.0 % - 7.1 %]	[0.2% - 6.7%]	[0.4% - 8.6%]	[0.8% - 9.6%]			
accuracy (+/-)	3.6%	3.8%	4.1%	4.4%			

Anticipating an attrition rate of 20% at 12 months, 125 subjects will be enrolled for this study.

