14.3 Statistical Analysis Endpoints

14.3.1 Primary Endpoint

Incidence of hernia recurrence within 12 months will be calculated on the FAS subjects who reach the 12-month follow-up including any subject with hernia recurrence diagnosed within the 12-month period following surgery (even if the subject has withdrawn from the study before the 12-month assessment).

The primary endpoint will be summarized using count, percentage, and the corresponding 95% confidence interval. Sub-group analyses on primary endpoints will be performed according to study needs and will be described in the Statistical Analysis Plan and the Clinical Study Report.

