7.2. General Methodology

Statistical analysis is descriptive; some subgroup comparative analyses may be run in addition to primary and secondary endpoints, to assess impact of demographic characteristics, risk-factors, hernia characteristics and/or surgical technique applied (including mesh characteristics).

Continuous variables will be summarized using counts, means, and standard deviations, medians, minimum, maximum and 95% confidence Interval (CI). Categorical variables will be summarized using frequencies, percentages and 95% confidence interval (CI).

Statistical analysis will be implemented on overall subjects, using several analysis sets, as described previously (Section 7.1.3).

Several comparative analyses will be performed by hernia type (primary hernia versus incisional hernia) on overall subjects and on a subgroup of subjects with robotically assisted laparoscopic repair. Results of subjects operated with robotically assisted laparoscopic repair will also be compared with subjects operated with a traditional laparoscopic procedure. The following statistical tests will be used:

- Pearson Chi-square test or Exact test will be used (as appropriate) for categorical data
- Student t-test or Wilcoxon rank sum test will be used if assumptions or t-test are not verified for continuous data.

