7.5. Adjustments for Multiple Comparisons

Statistical analysis of primary and secondary endpoints is descriptive. No adjustment will be done.

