7.9. Evaluation of Objectives

Study objectives will be assessed through study endpoints measurement.

The primary endpoint is incidence of hernia recurrence within 12 months following Parietene[™] DS Composite Mesh use in ventral hernia repair.

Incidence of hernia recurrence within 12 months will be measured on the FAS subjects and using the following calculation formula:

[Subjects with Recurrence diagnosed within the first 12month following surgery]

[Subjects with Recurrence diagnosed within the first 12month following surgery + Subjects free of recurrence with a follow-up ≥12months]

A confirmatory analysis of primary endpoint will be run using Per Protocol Analysis Set.

Secondary endpoints

- Incidence of adverse device effects (ADEs) intra-operatively, at discharge, within 1 month, 3 months, 12 months, and 24 months following Parietene[™] DS Composite mesh use in ventral hernia repair will be primarily assessed based on FAS, and secondarily using PPAS and SAS.
- Incidence of hernia recurrence at 1, 3 and 24 months. The evaluation of hernia recurrence will be performed during a physical examination, using the formula described previously, according to the different time-points, and based on FAS and PPAS.
- Time to hernia recurrence and time to adverse device effect occurrence (from surgery time-point), will be assessed using Kaplan Meyer estimates. FAS and PPAS will be used for time to hernia recurrence, while FAS, PPAS and SAS will be used for time to ADE occurrence analysis. Time to Device-related AEs occurrence may also be assessed using Kaplan Meyer estimates.
- Carolinas Comfort Scale[™] QOL questionnaires completed pre-operatively and at 1, 12 and 24 months postoperatively will be analyzed using the Carolina Comfort Scale User Guide recommendations and programming code (see Appendix B), and based on FAS and on PPAS.

Several Subgroup analyses will be performed. Comparative analyses will be performed by hernia type (primary hernia versus incisional hernia) on overall subjects and on a subgroup of subjects with robotically assisted laparoscopic repair. Results of subjects operated with robotically assisted laparoscopic repair will also be compared with subjects operated with a traditional Laparoscopic procedure.

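### The precision table prints an upper limit of 6.7% where its own ±3.8% gives 7.8%; its Wald limits are somewhat too favourable, and no interval method is named for the analysis

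*Protocol*

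**What the plan says.** Protocol 14.5 bases the sample size on how precisely the 12-month recurrence rate can be estimated. It takes planning rates of 3.5% to 5.2% from earlier studies of the predicate mesh and introduces the table with "95% confidence intervals obtained from incidence rates between 3.5% and 5.2% with N=100 subjects are shown below". SAP section 6 repeats the table with the same figures:

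| Rate | 3.5% | 4.0% | 4.5% | 5.2% |
|---|---|---|---|---|
| Printed 95% CI | 0.0 to 7.1 | 0.2 to 6.7 | 0.4 to 8.6 | 0.8 to 9.6 |
| Printed accuracy (±) | 3.6 | 3.8 | 4.1 | 4.4 |

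With 20% attrition, 100 evaluable subjects become 125 enrolled. The Protocol synopsis carries the same table, but the upper limit of its 4.0% cell could not be read in the text available for this review.

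For the analysis, Protocol 14.3.1 says "The primary endpoint will be summarized using count, percentage, and the corresponding 95% confidence interval". SAP 7.2 asks for a 95% interval for categorical variables, without a method. SAP 7.9 defines the estimate ("Incidence of hernia recurrence within 12 months will be measured on the FAS subjects and using the following calculation formula") and gives numerator and denominator, but no interval. The exact test named in SAP 7.2 is for subgroup comparisons, not for the interval of a single proportion. SAP 7.5 adds that "Statistical analysis of primary and secondary endpoints is descriptive".

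**The concern.** There are three linked points.

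1. One cell contradicts its own column. The printed upper limits run 7.1, 6.7, 8.6, 9.6, so they fall as the rate rises from 3.5% to 4.0%.
2. The rest of the table looks like the simple normal-approximation (Wald) interval. That interval performs poorly when only about 3 to 5 events per 100 are expected. A sign of strain is the 3.5% lower limit, which is negative before it is cut to 0.0%.
3. If no method is named, the Wald table is the only guide to what will be reported for the primary endpoint.

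This is a single-arm study without a hypothesis test, so the interval carries most of the inferential content of the primary result. The precision table is also the only justification offered for the sample size. Both should be correct and should mean 95% when they say 95%.

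**Working it through.** **Inputs.** N=100 and rates 3.5, 4.0, 4.5 and 5.2% (Protocol 14.5, SAP section 6). Sidedness is not stated; I assume two-sided 95%, z=1.96, which the printed figures support.

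**Step 1: reproduce the table.** Wald: p ± 1.96·√(p(1−p)/100). At 4.0%: 1.96·√(0.04·0.96/100) = 0.0384, giving 0.16% to 7.84%.

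| Rate | Wald half-width | Wald limits | Printed |
|---|---|---|---|
| 3.5% | 3.60 | −0.10 to 7.10 | 0.0 to 7.1 |
| 4.0% | 3.84 | 0.16 to 7.84 | 0.2 to **6.7** |
| 4.5% | 4.06 | 0.44 to 8.56 | 0.4 to 8.6 |
| 5.2% | 4.35 | 0.85 to 9.55 | 0.8 to 9.6 |

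All four half-widths and seven of the eight limits reproduce, with the 3.5% lower limit cut at zero. Only 6.7% does not.

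**Step 2: could another method give 6.7%?** Upper limits at 4/100 are: 90% Wald 7.2, continuity-corrected Wald 8.3, Jeffreys 9.2, Wilson 9.8, Clopper-Pearson 9.9, Agresti-Coull 10.2. None gives 6.7. An upper limit of 6.7% needs a half-width of 2.7 points, hence N = 1.96²·0.04·0.96/0.027² ≈ 202. The cell is a slip.

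**Step 3: better intervals at the same rates.**

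- Wilson: [p + z²/2n ± z·√(p(1−p)/n + z²/4n²)] / (1 + z²/n). At 4.0%: (0.0592 ± 0.0429)/1.0384 = 1.57% to 9.84%.
- Clopper-Pearson: the 0.025 quantile of Beta(x, n−x+1) and the 0.975 quantile of Beta(x+1, n−x). At x=4: 1.10% to 9.93%. For 3.5, 4.5 and 5.2% the count is not whole, so those values are interpolations for planning only.

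| Rate | Wilson limits (half-width) | Clopper-Pearson limits (half-width) | Upper limit above Wald |
|---|---|---|---|
| 3.5% | 1.29 to 9.15 (3.93) | 0.85 to 9.23 (4.19) | 2.05 / 2.13 |
| 4.0% | 1.57 to 9.84 (4.14) | 1.10 to 9.93 (4.41) | 2.00 / 2.08 |
| 4.5% | 1.86 to 10.51 (4.33) | 1.36 to 10.61 (4.62) | 1.95 / 2.05 |
| 5.2% | 2.28 to 11.44 (4.58) | 1.76 to 11.55 (4.90) | 1.89 / 2.00 |

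**Step 4: exact coverage at N=100**, summing binomial probabilities over x = 0 to 100.

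| True rate | Wald | Wilson | Clopper-Pearson | Wald interval wholly below the truth |
|---|---|---|---|---|
| 3.5% | 86.6% | 97.6% | 97.6% | 13.1% |
| 4.0% | 90.6% | 93.6% | 96.4% | 8.7% |
| 4.5% | 93.7% | 95.3% | 97.5% | 5.7% |
| 5.2% | 89.2% | 96.0% | 98.0% | 10.3% |

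The one-sided misses can be checked by hand. With one recurrence the Wald upper limit is 1.0 + 1.95 = 2.95%, and with none the interval collapses to 0% to 0%. At a true 3.5% both outcomes miss: 0.965¹⁰⁰ + 100·0.035·0.965⁹⁹ = 0.028 + 0.103 = 0.131. The Wald interval therefore errs mainly by understating recurrence. With zero events Clopper-Pearson gives 0% to 1 − 0.025^(1/100) = 3.6%.

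**Step 5: sample size.** 100/(1 − 0.20) = 125, which does not involve the wrong cell.

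**The case against.** The best defence is that nothing in the design rests on the wrong cell. The sample size is tied to the accuracy row and the ±3.6% to ±4.4% range. All four accuracy figures are right for Wald, 6.7% is not an end point of that range, and 125 follows from 100/0.8. All of this stands.

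On method, a symmetric half-width at assumed rates is a planning display. The documents set no target width and no recurrence threshold, so Wald breaks no rule of theirs. The half-width cost is small: 0.2 to 0.3 points with Wilson, 0.5 to 0.6 with Clopper-Pearson. Neither alternative gives exactly 95%: Wilson dips to 93.6% at 4.0%, and Clopper-Pearson runs at 96.4% to 98.0%. Wald coverage also oscillates with the rate, so 86.6% is the low point of the four. These are fair limits on the size of the point, and under-coverage would reach the results only if Wald were also used in the analysis.

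They do not remove it. Wald is below 95% at all four planning rates, the misses are almost all in the direction that flatters the device, and about 2 points on an upper limit of 7% to 10% is visible to a reader. Nor do they answer the missing method, which leaves that difference to be settled at analysis.

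**Conclusion.** The concern holds on all three parts.

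- **Slip:** 6.7% should be 7.8%. This is a 1.1-point error in one cell, present in Protocol 14.5 and SAP section 6.
- **Method in the table:** Wald limits make the stated precision somewhat too favourable. Half-widths are 3.6 to 4.4 points, against 3.9 to 4.6 (Wilson) or 4.2 to 4.9 (Clopper-Pearson). Upper limits are about 2 points too low, and coverage is 86.6% to 93.7%.
- **Analysis:** no interval method is specified for the primary proportion.

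The figures assume two-sided 95% intervals, exactly 100 evaluable subjects and the documents' four planning rates. The effect is on the stated precision and the interval to be reported. It does not touch enrolment or any decision rule. It should be fixed, but it does not threaten the study.

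**What to change.** 1. Change 6.7% to 7.8% in Protocol 14.5 and SAP section 6, and check the same cell in the Protocol synopsis.
2. Add one sentence to SAP 7.9 naming a single interval method, Wilson or Clopper-Pearson, for the primary recurrence proportion and for the other recurrence and ADE proportions. Clopper-Pearson is the natural choice if coverage of at least 95% is wanted; Wilson is slightly narrower.
3. Preferably, recompute the table by that method and give asymmetric limits, for example 1.1% to 9.9% for 4/100 by Clopper-Pearson.

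Items 1 and 2 cost one cell per table and one SAP sentence. Item 3 also changes the accuracy row and the sentence giving the ±3.6% to ±4.4% range, wherever the table appears, and the stated precision becomes slightly less favourable. Protocol 16.6 sends amendments through sponsor and IRB review, so the table changes are best bundled with another amendment. Protocol 14.1 lets changes to the planned analysis be documented in the SAP, so item 2 need not wait. Enrolment stays at 125.

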14.6 Handling of Missing Data

No data imputation will be performed for missing data unless otherwise noted in statistical analysis plan. All practical monitoring and follow-up steps will be taken to ensure complete and accurate data collection.

15. Ethics

15.1 Statement(s) of Compliance

This clinical investigation will be conducted in accordance with the protocol, with the ethical principles that have their origin in the Declaration of Helsinki, Good Clinical Practice guideline and any regional or national regulations such as FDA regulations (US), as appropriate. All principles of the Declaration of

MDT17051PDS Version 4.0 Page 44 of 56

Helsinki have been implemented in this clinical study by means of the subject informed consent process, IRB approval, clinical study training, clinical study registration, publication policy.

Ultimately, all study sites in all geographies will follow and comply with:

- 21 CFR Part 11 (Electronic Records, Electronic Signatures)
- 21 CFR Part 50 (Protection of Human Subjects)
- 21 CFR Part 54 (Financial Disclosure by Clinical Investigators)
- 21 CFR Part 56 (IRBs)
- 21 CFR Part 803 (Medical Device Reporting)
- The CTA
- Procedures described within this CIP
- Local EC Requirements

The clinical investigation will not begin until all necessary approvals/favorable opinions are obtained from the appropriate IRB. Should an IRB impose any additional requirements, they will be followed.

Information regarding the study and study data will be made available via publication on clinicaltrials.gov. Additionally, the results of this study will be offered for publication at the conclusion of the study, if participating investigator(s) believe the data warrants publication in an appropriate journal.

16. Study Administration

16.1 Monitoring

Site visits will be conducted by authorized Medtronic representative(s) to qualify potential sites, conduct site initiation, ensure compliance, assess informed consent process, conduct interim monitoring visits to monitor study data, subjects' medical records, eCRFs, device accountability, device use and storage, IRB submissions, regulatory binder in accordance with current protocol, ICH, GCPs and the respective local and national regulations and guidelines (if applicable) as well as close-out site activities. The Study Investigator(s) and the investigating site will permit authorized clinical research personnel from Medtronic or contracted by Medtronic to review completed eCRFs, IRB decisions, and Investigator and clinical site records at regular intervals throughout the study as well as permit study-related monitoring, audits, IRB review, and regulatory inspection(s) by providing direct access to source data/documents per the monitoring plan. Additionally, subject charts and clinical records will be requested and reviewed so that protocol adherence and source documentation can be verified. In instances where data protection regulations prohibit the direct examination of hospital records by the

MDT17051PDS Version 4.0 Page 45 of 56

study Sponsor or designee(s), the Investigator(s) will cooperate in a system of source data verification with the Sponsor. Monitoring may be performed with in person visits or remotely, when applicable.

To ensure the rights, safety, and welfare of study subjects are being maintained, the monitor will maintain assurance that all study staff are trained on the study protocol and use of the study devices. If the monitor discovers that an investigator is not complying with the signed Investigator Agreement, the

investigational plan, applicable laws, or any conditions of approval imposed by the reviewing IRB, the monitor will report to the Sponsor and take such steps necessary to promptly secure compliance. If compliance cannot be secured, device shipments to the investigator may be discontinued and the investigator's participation in the investigation terminated. The monitor shall also require such an investigator to dispose of or return the device, unless this action would jeopardize the rights, safety, or welfare of a subject.

16.2 Data Management

Data review will be performed to identify possible data discrepancies. Manual and/or automatic queries will be created in the Oracle® Remote Data Capture (RDC) system and will be issued to the site for appropriate response. The site staff will be responsible for resolving all queries in the database. Adverse Events will be coded per Medical Dictionary for Regulatory Activities (MedDRA).

This study will be using a 21 CFR Part 11 compliant electronic data capture system. All system level validation documentation is retained within the Medtronic Information Systems group.

16.3 Direct Access to Source Data/Documents

Investigator(s)/institution(s) will permit study-related monitoring, audits, IRB review, and regulatory inspection(s), and provide direct access to source data/documents as per local policies and regulations.

16.4 Confidentiality

All records identifying the subject will be kept confidential and, to the extent permitted by the applicable laws and/or regulations, will not be made publicly available.

Subject names will be kept confidential. Only the site identification number and subject number will be recorded in the eCRFs, and if the subject name appears on any other document, it must be redacted.

Study findings stored on a computer will be stored in accordance with local data protection laws. The subjects will be informed in writing that representatives of the sponsor, IRBs, or Regulatory Authorities may inspect their medical records to verify the information collected, and that all personal information made available for inspection will be handled in strictest confidence and in accordance with local data protection laws. Subjects will also be informed that information regarding the study that does not include subject identifiers will be posted on clinicaltrials.gov.

MDT17051PDS Version 4.0 Page 46 of 56

When the results of the study are published, the subject's identity will remain confidential. The investigator will maintain a master subject list to enable subjects' records to be identified.

16.5 Liability

Medtronic maintains appropriate clinical study liability insurance coverage as required under applicable laws and regulations and will comply with applicable local law and custom concerning specific insurance coverage. If required, a clinical study insurance statement/certificate will be provided to the IRB.

16.6 Clinical Investigation Plan (CIP) / Protocol Amendments

A CIP/Protocol amendment will be prepared when there are revisions that are significant changes or corrections, or modifications that impact subject safety, ethical conduct, data integrity or study design. CIP/Protocol amendments must undergo review and approval by the sponsor, IRB, and any appropriate regulatory authority, and will be logged in the document version history (Section 18). IRB approval, regulatory authority approval (if applicable), site training and a new Acknowledgement form will be signed and returned before any new enrollment takes place.

16.7 Record Retention

The investigator(s) and the sponsor will maintain the records of the study including all pertinent correspondence, the study protocol with any/all amendments, all correspondence with and approval from the IRB, the Investigator Agreement, device accountability records, individual subject records, and signed informed consent forms. Subject files, other source data and essential documentation kept in the Investigator study files, must be kept for a period of no less than 24 months after the latter of the following two dates: the date on which this investigation is terminated or completed. Records may need to be maintained by the Principal Investigator for a longer duration if national regulations require or if agreed to in writing with Medtronic. All data and documents should be made available if requested by relevant authorities.

16.8 Publication and Use of Information

The Medtronic Publication and Authorship Policy is aligned with the International Committee of Medical Journal Editors (ICMJE) recommendations (www.icmje.org). Medtronic will seek to publish, in appropriate peer-reviewed journals and scientific conferences, results of clinical studies where human subjects are involved, regardless of outcome. While study results are owned by Medtronic, all data on which a publication is based will be made available to all authors as required for their participation in the publication process. Furthermore, data may be published or used by study investigator(s) provided that such publication or use is in accordance with this protocol, the Medtronic Publication and Authorship Policy, and the Clinical Investigation Agreement. Investigator(s) must submit a copy of all manuscripts and/or abstracts to Medtronic for review and comment 30 days prior to planned submission. Medtronic acknowledges that its right to review and comment shall relate solely to the

MDT17051PDS Version 4.0 Page 47 of 56

proprietary, licensing, and/or confidential rights Medtronic may have in such proposed publication, rather than whether such results and/or opinions are favorable to Medtronic.

The publication of post-hoc analyses, regional results, or single-center experiences based on multicenter clinical studies should not precede that of the primary multicenter publication, and should cite the primary publication whenever possible, as required by specific journal and scientific meeting guidelines.

Medtronic involvement in a publication (e.g., funding of the study; sponsor of the study; collection, analysis, and interpretation of data; professional writing assistance) must be disclosed according to journal-specific policies, submission requirements, and prevailing editorial standards, in addition to those specified by International Committee of Medical Journal Editors. Authors must ensure that an acknowledgement/disclosure statement is included in the body of the manuscript for Medtronic to review for accuracy. All authors must also disclose financial or personal affiliations that could be considered conflicts of interest as per journal/conference requirements.

To enable health care providers, payers, and subjects' access to the wealth of Medtronic's research, Medtronic will report its scientific data in accordance with the principles outlined in the Guidance Document on Registration and Reporting Results of Company-Sponsored Clinical Trials under FDAAA 2007 (Title VIII).

